5.2.9 Tuberculosis screening and monitoring

5.2.9.1 Screening evaluation

A blood test for TB will be done at screening using QFT-G. This is an interferon-gamma release assay (IGRAs) test. Evaluation of all subjects by QFT-G test (to be performed by the central clinical laboratory) and chest X-rays must be completed prior to randomisation. Refer

Section 3.1, inclusion criteria 16 (d) (iii) and (e). If an adequate (posterior-anterior or anterior-posterior and lateral posterior-anterior, unless limited by local practice) chest X-ray has been performed within 12 weeks prior to signing the ICF, it does not need to be repeated at the screening visit.

Compared to culture confirmed TB, overall, 87.6% of subjects have a positive QFT-G result (Cellestis, 2005). The false negative rate in this setting appears to be over 12%. Further, the performance of the test in the setting of immunosuppressant drugs has not been evaluated. Nor has it been evaluated in individuals with medical conditions other than, or in addition to, latent TB or TB disease. The guide also states that “Medical treatments or conditions that impair immune functions can potentially reduce IFN- γ responses and prevent detection of a specific response to the (secretory proteins) ESAT-6 and CFP-10 (the test stimulators)”.

Given the population to be enrolled in the LN study, false negative tests are possible, so a chest X-ray, posterior-anterior or posterior-anterior and lateral views is a relevant technique and warranted technique (unless limited by local practice) for detecting active pulmonary disease and minimising potential risk to study subjects.

5.2.9.2 Tuberculosis results from screening evaluations

- If the screening QFT-G test is negative and there is no known history of recent exposure to individuals with active TB, and chest radiograph shows no evidence of active TB, the subject may be randomised without prophylaxis.
- If the screening QFT-G test is **newly positive*** and the chest radiograph shows no evidence of active TB, and the subject has no symptoms or medical history consistent with active TB, treatment for latent TB must be initiated prior to the first IP administration and the subject must commit to completing the full duration of prophylaxis, which may mean completing prophylaxis during the study. Subjects may be re-screened if necessary to allow for local guidelines on latent TB treatment initiation.

*Note: Newly positive can be a positive result after a previous indeterminate or negative result.

- If the QFT-G test is positive at screening but the subject is **not newly positive**, the subject may be randomised if:
 - Previous or current active TB infection was ruled out **and**
 - The subject was previously diagnosed with latent TB and has documentation confirming completion of appropriate latent TB infection treatment or

- The subject was previously diagnosed with latent TB and is currently receiving prophylactic treatment for latent TB and commits to completing the full duration of prophylaxis
- If the screening QFT-G test is indeterminate, the test must be repeated at least one time by the central laboratory as soon as possible. The subject may be randomised if:
 - If the QFT-G test result remains indeterminate or becomes negative and
 - The chest radiograph shows no evidence of active TB and
 - There are no signs or symptoms of active TB and
 - There is no known recent close contact with anyone with active TB and
 - There is no history of latent TB (unless diagnosed with documentation of completion of appropriate treatment) or active TB

Additionally, an expert specialising in TB may be consulted prior to randomisation, if deemed necessary in the opinion of the Investigator, after discussion with the Sponsor/Designee Medical Monitor. If the subject is randomised, additional QFT-G testing will be performed according to the Study Plan ([Table 2](#), [Table 3](#), [Table 4](#), and [Table 5](#)).

5.2.9.3 Tuberculosis monitoring during the study

If, during the study, a subject who had an indeterminate TB result at screening is determined to have a:

- Positive QFT-G test result, confirm positive QFT-G on another blood sample and then the subject should be referred to a TB specialist. If a TB specialist is not available, the local country guidelines should be followed for further diagnostic work up and anti-TB treatment regimens. If no local guidelines exist for immunocompromised individuals, then CDC guidelines may be followed. This should also be reported as an AESI. Once latent TB is confirmed, treatment must be instituted immediately and no IP may be administered until treatment of latent TB has begun
- Negative QFT-G test result, then the subject does not need to continue TB testing outlined for subjects with indeterminate results at screening

- Indeterminate QFT-G test result, then the subject will continue in the study and TB testing will be performed as outlined for subjects with indeterminate results at screening

End of treatment testing for subjects with negative QFT-G at baseline and no symptoms of active TB.

For subjects not continuing in second year extension period:

- Week 52 QFT-G negative: no further testing.
- Week 52 QFT-G indeterminate: repeat at Week 56. If negative no further testing, however if indeterminate repeat again at last visit Week 60.
- QFT-G positive at Week 52 or later. Confirm positive QFT-G on another blood sample. If confirmed follow recommendations for positive QFT-G results during study. If repeat test is indeterminate or negative follow recommendation for indeterminate results above. Consider referral to TB specialist.

For subjects continuing in second year extension period:

- Week 104 QFT-G negative: no further testing.
- Week 104 QFT-G indeterminate: repeat at Week 108. If negative no further testing, however if indeterminate repeat again at last visit Week 112.
- QFT-G positive at Week 104 or later. Confirm positive QFT-G on another blood sample. If confirmed follow recommendations for positive QFT-G results during study. If repeat test is indeterminate or negative follow recommendation for indeterminate results above. Consider referral to TB specialist.

Tuberculosis questionnaire

To aid in the early detection of new or reactivated TB, a TB questionnaire will be used to evaluate subjects for signs and symptoms of TB at every visit prior to receiving IP. If the evaluation raises suspicion that a subject may have new or reactivated TB, an immediate and thorough investigation should be undertaken including, where possible, consultation with experts specialising in TB.

Investigators should be aware that TB in immunocompromised subjects may present as disseminated disease or with extra-pulmonary features and should be referred for appropriate treatment.

5.2.10 Safety laboratory tests

The following are the laboratory-based safety assessments:

- Screening laboratory tests
- Haematology
- Serum chemistry
- Lipid profile
- Urine analysis
- Pregnancy tests

A Laboratory Manual will be provided to the sites that specifies the procedures for collection, processing, storage, and shipment of samples, as well as laboratory contact information, specific to this clinical research study.

All clinical laboratory tests will be performed in a central clinical laboratory at the times indicated in the Study Plan ([Table 2](#), [Table 3](#), [Table 4](#), and [Table 5](#)).

A serum pregnancy test (or serum FSH in post-menopausal females with menses absent for ≥ 1 year) will be performed at screening at the central laboratory. If the result of the serum β hCG test is borderline or thought to be false positive the test can be repeated during the screening. The subject can continue if the repeat test is negative. At every visit after screening, urine pregnancy tests will be performed at the site using a dipstick. During the treatment period, urine pregnancy tests should be performed at each visit before administering the IP and Sponsor-provided MMF. Abnormal safety laboratory results should be repeated as clinically indicated, as soon as possible (preferably within 24 to 48 hours).

Additional safety samples may be collected if clinically indicated at the discretion of the Investigator.

Every attempt should be made to redraw any missing safety or efficacy laboratory tests, even if the subject has received the IP.

The Investigator should make an assessment of the available results with regard to clinically relevant abnormalities. The laboratory results should be signed and dated and retained at the centre as source data for laboratory variables. For information on how AEs based on laboratory tests should be recorded and reported, see Section 6.5.

In case a subject shows an AST or ALT $\geq 3 \times \text{ULN}$ or total bilirubin $\geq 2 \times \text{ULN}$ please refer to [Appendix D](#) 'Actions required in cases of combined increase of Aminotransferase and Total Bilirubin – Hy's Law', for further instructions.

The laboratory variables that will be measured are summarised in Table 6.

Table 6 Clinical laboratory tests

Screening only test

Haemoglobin A1c (HbA1c; diabetic subjects only)

Peripheral blood B lymphocyte count (CD19+ cells)-Only for subjects who received rituximab or other B cell-depleting therapy >26 weeks prior to signing ICF (see exclusion criterion No. 17)

HbsAg

HBcAb (reflex DNA testing if isolated HBcAb positive)

Hepatitis C antibody

HIV test

TB screening

QFT-G test (repeat test if result is indeterminate, as per [Table 2](#) and [Table 4](#))

Coagulation panel

Activated partial thromboplastin time, Prothrombin Time, INR

Haematology

WBC count with differential

RBC count

Haematocrit

Haemoglobin

Platelet count

MCV

MCHC

Serum chemistry

Calcium

Chloride

Potassium

Sodium

Bicarbonate

AST*

ALT*

ALP*

GGT

BUN

Creatinine

eGFR (calculated)

Total bilirubin* (reflexively fractionated if elevated)

Glucose

Albumin

CK

*Note for serum chemistry: Tests for AST, ALT, ALP, and total bilirubin must be conducted concurrently and assessed concurrently.

Immunology

Immunology profile: ANA, anti-RNP antibody, anti-Smith antibody, anti-Sjogren's Syndrome A [SSA] and anti-Sjogren's Syndrome B [SSB] antibodies; anti-cardiolipin antibodies (IgA, IgM and IgG), and quantitative total immunoglobulin testing (IgA, IgG, IgM)

Lupus serology tests (C3 and C4 complement, anti-ds DNA)

Urinalysis

Colour

Clarity

Specific gravity

pH

Protein

Glucose

Ketones

Blood

Bilirubin

Microscopy including WBC/HPF, RBC/HPF, cellular casts

Spot urine creatinine and protein, urine protein/creatinine ratio

24-hour urine creatinine and protein, UPCR

Pregnancy test

Serum β -hCG (at screening only)

Urine β -hCG (at every visit after screening, using a dipstick)

Serum FSH (at screening only) in post-menopausal females with menses absent for ≥ 1 year

ALP=alkaline phosphatase; ALT=alanine transaminase; ANA=antinuclear antibody; anti-RNP=anti-ribonucleoprotein; AST=aspartate transaminase; β -hCG= β -human chorionic gonadotropin; BUN=blood urea nitrogen; C3=third component of complement; C4=fourth component of complement; CK=creatine kinase; DNA=deoxyribonucleic acid; eGFR=estimated glomerular filtration rate; GGT=gamma glutamyl transferase; HbA1c=glycosylated haemoglobin; HbCAb=hepatitis B core antibody; HbsAg=Hepatitis B surface antigen; HPF=high power field; HIV=human immunodeficiency virus; INR=International normalised ratio; MCHC=mean corpuscular haemoglobin concentration; MCV=mean corpuscular volume; QFT-G=QuantiFERON-TB Gold; RBC=red blood cell; WBC=white blood cell

Note: If central laboratory results are not available for SLEDAI-2K associated tests, samples should be redrawn one time within 14 days of the SLEDAI assessment date.

A reflex test is a test that is must be performed based on the results of a prior test (pre-set criteria).

5.2.10.1 Laboratory assessments for cardiovascular risk assessments

Subjects will have a fasting lipid profile (cholesterol, high density lipoprotein cholesterol, low density lipoprotein cholesterol, and triglycerides) completed at times indicated in the Study Plan (Table 2 and Table 4). Subjects will be required to fast for at least 8 hours prior to this assessment (see Section 3.8).

5.2.11 Immunological tests

5.2.11.1 Immunology profile

Subjects will have tests to determine immunology profile (ANA, anti-Smith, anti-RNP, anti-SSA, anti-SSB, and anti-cardiolipin antibodies), and quantitative immunoglobulins (IgA, IgG, IgM) completed at times indicated in the Study Plan (Table 2 and Table 4).

5.2.11.2 Lupus serology

Anti-dsDNA antibodies and complement C3 and C4 levels are commonly used as markers of SLE and of LN disease activity and comprise the serologic domain of the SLEDAI-2K. Subjects will have these tests performed at the times indicated in the Study Plan (Table 2, Table 3, Table 4, and Table 5).

5.2.11.3 Anti-drug antibodies

Instructions for immunogenicity (ADA and ADA neutralising antibodies [nAb]) sample collection, processing, storage, and shipment can be found in the separate Laboratory Manual provided to the centres.

The pre-dose serum samples to measure the presence of ADA will be collected according to the Study Plan (Table 2, Table 3, Table 4, and Table 5). The presence or absence of ADA will be determined in the serum samples using validated bioanalytical methods.

5.2.11.4 Neutralising antibodies

Neutralising antibodies testing will only occur in samples that are ADA positive. Samples that are ADA negative will not be tested for nAb. The presence or absence of nAb will be determined using a validated bioanalytical method.

5.2.12 Mycophenolic acid levels

The blood samples will be collected to explore trough MPA concentration in LN subjects. Relationship of MPA concentrations and AEs possibly related to MPA may also be explored. Serum samples for the determination of trough MPA levels will be collected at the times indicated in the Study Plan (Table 2). MPA concentrations will be analysed by a central laboratory on behalf of the Sponsor, using a validated bioanalytical method. The dose of MMF should be withheld until samples for the MPA blood draw test has been collected on that visit day.

5.3 Other assessments

5.3.1 Quality of life/pharmacoeconomic assessments

5.3.1.1 Patient Global Assessment

Subjects will be asked to complete the PtGA at the times indicated in the Study Plan (Table 2, Table 3, Table 4, and Table 5). The PtGA is a single-item question that takes into account “all the ways that your illness affects how you are doing” over the last week. Responses range from 0 (very well) to 100 (very poor) on a 100 mm VAS. The subject must complete the PtGA (see Appendix T).

5.4 Pharmacokinetics

5.4.1 Collection of samples

For the PK analysis it is important that the date, start and stop time for the IV infusion, and the sample collection time are recorded. Instructions for sample collection, processing, storage, and shipment can be found in the separate Laboratory Manual provided to the centres. Serum will be collected according to the Study Plan (Table 2, Table 3, Table 4, and Table 5). Post-dose samples should be collected 15 minutes \pm 5 minutes after completion of IP infusion. It must be noted that the duration of the IV infusion for administering the IP will be no less than

60 minutes for the first 3 doses (Visits 1, 2 and 3) and no less than 30 minutes, starting with Visit 4.

Samples will be collected, labelled stored and shipped as detailed in the Laboratory Manual.

5.4.2 Determination of drug concentration

Samples for determination of drug concentration in serum will be analysed by PPD on behalf of AstraZeneca, using an appropriate bioanalytical method. Full details of the analytical method used will be described in a separate bioanalytical report.

5.4.3 Storage and destruction of pharmacokinetic samples

Samples may be stored for up to 15 years or as per local regulation from the date of the last subject last visit (LSLV), after which they will be destroyed.

5.5 Pharmacodynamics

Type I IFN-inducible signature in whole blood, as assessed by a 21-gene assay, will be used as a PD marker to follow the biologic effect of anifrolumab on its target throughout the study.

5.5.1 Collection of samples

Whole blood will be collected for mRNA isolation at the visits indicated in the Study Plan ([Table 2](#), [Table 3](#), [Table 4](#), and [Table 5](#)) in order to evaluate the mRNA expression levels of 21 Type I IFN-inducible genes. The remaining mRNA from the PD sample may be utilised for additional biomarker work to further characterise the effects of anifrolumab on its target. For detailed method descriptions refer the reader to the Laboratory Manual.

5.5.2 Storage, re-use and destruction of pharmacodynamic samples

Samples collected for PD analysis may be stored for a maximum of 15 years from the date of the LSLV, or as per the local regulations, after which they will be destroyed.

5.6 Genetics

There will be no mandatory genetic samples collection for this study.

5.6.1 Pharmacogenomics (optional)

DNA from blood for genetic studies will be collected at baseline. DNA from blood for epigenetic studies will be collected at Week 0, Week 24 and Week 52. All genetic analyses will be limited to understanding LN or the efficacy and toxicity of anifrolumab and SOC. Analyses will include but may not be limited to single nucleotide polymorphism profiling, copy number variation analysis and epigenetic profiling by microarray.

The collection of blood for pharmacogenomic analyses is optional. A separate ICF is required for these samples. The results from these investigations will not be reported in the CSR but in

separate reports and in scientific publications as appropriate. Pharmacogenomics will not be included in the second year extension period.

5.7 Biomarker analysis

The subject's consent to the use of donated biological samples has to be taken. Biological samples (blood, urine, and tissue) will be collected and may be analysed for exploratory biomarkers to assess correlations with disease activity, effects of study drug, clinical outcomes and toxicity.

The purpose of these tests is to gain a better understanding of LN, the role of IFNs in LN, the impact of anifrolumab on LN related abnormalities and to identify biomarker candidates with potential clinical applications in LN. The results from these investigations will not be reported in the CSR but in separate reports and in scientific publications as appropriate.

5.7.1 Serum and plasma biomarkers

Serum and plasma samples will be collected for mechanistic studies during the visits specified in the Study Plan ([Table 2](#), [Table 3](#), [Table 4](#), and [Table 5](#)). These studies may include soluble analytes, such as proteins, antibodies, peptides and immune complexes and will be conducted using a variety of technical approaches such as immunoassays, protein arrays, in vitro assays, and/or biochemical methods. The results from these investigations will not be reported in the CSR but in separate reports and in scientific publications as appropriate.

5.7.2 Urine biomarkers

Urine samples will be collected for mechanistic studies during the visits specified in the Study Plan ([Table 2](#) and [Table 3](#)). These studies may include soluble analytes such as proteins, peptides, antibodies and immune complexes and will be conducted using a variety of technical approaches such as immunoassays, protein arrays, in vitro assays, and/or biochemical methods. The results from these investigations will not be reported in the CSR but in separate reports and in scientific publications as appropriate. Urine biomarkers will not be assessed in the second year extension period.

5.7.3 RNA transcript profiling

To better understand the impact of Type-1 interferon blockade on systemic immune processes whole blood samples will be collected as indicated in the Study Plan ([Table 2](#), [Table 3](#), [Table 4](#), and [Table 5](#)) for retrospective analyses of genome wide transcriptome profiling. Transcriptome profiles will be assessed as potential markers predictive of response or as additional PD response biomarkers. The results from these investigations will not be reported in the CSR but in separate reports and in scientific publications as appropriate.

5.7.4 Interferon test in whole blood

Whole blood will be collected at screening in PAXgene tubes to measure the over expression of mRNA for certain types of type I IFN-inducible genes using a 4-gene test. The IFN test and the data will be evaluated for development of a companion diagnostic.

The primary intent of this test is to prospectively identify subjects with interferon “test-high” or interferon “test-low” for the purpose of randomisation. The results of this test will be used to stratify subjects. The kit uses the expression of the genes IFI27, IFI44, IFI44L and RSAD2 compared with 3 reference genes; 18S, ACTB and GAPDH. The result is expressed as a score that is compared with a pre-established cut-off to classify subjects into 2 groups: low or high levels of IFN-inducible gene expression. The results of the test will not be used to determine eligibility and will not be shared with the investigative site (ie, all site personnel will remain blinded to IFN test results).

5.7.5 Tissue biomarkers: immunostaining, epigenetic and gene expression studies on renal biopsies (optional)

These tests are in addition to the standard evaluation of renal biopsies and require a separate ICF. These studies will be done from existing clinical biopsy material (eg, fixed paraffin embedded tissue). The studies will be limited to gain better understanding about the pathogenesis and the role of IFN in LN. A variety of techniques may be used, such as immunostaining for various inflammatory markers and gene expression and epigenetic analysis. The results from these investigations will not be reported in the CSR but in separate reports and in scientific publications as appropriate.

5.7.6 Storage, re-use and destruction of biological samples

Samples may be stored for a maximum of 15 years from the date of the LSLV, or as per local regulation, after which they will be destroyed.

5.7.7 Labelling and shipment of biological samples

The Principal Investigator ensures that samples are labelled and shipped in accordance with the Laboratory Manual and the Biological Substance, Category B Regulations (see [Appendix B](#), ‘IATA 6.2 Guidance Document’).

Any samples identified as Infectious Category A materials are not shipped and no further samples will be taken from the subject unless agreed with AstraZeneca and appropriate labelling, shipment and containment provisions are approved.

5.7.8 Chain of custody of biological samples

A full chain of custody is maintained for all samples throughout their lifecycle.

The Principal Investigator at each centre keeps full traceability of collected biological samples from the subjects while in storage at the centre until shipment or disposal (where appropriate) and keeps documentation of receipt of arrival.

The sample receiver keeps full traceability of the samples while in storage and during use until used or disposed of or until further shipment and keeps documentation of receipt of arrival.

AstraZeneca keeps oversight of the entire life cycle through internal procedures, monitoring of study sites and auditing of external laboratory providers.

Samples retained for further use are stored at AstraZeneca R&D Mölndal Biobanken - [name] to be analysed at a facility to be selected by AstraZeneca at a later date, for up to 15 years or as per local regulation from the end of the study, which is expected to be in the third quarter of 2020. The samples will be destroyed after that.

5.7.9 Withdrawal of Informed Consent for donated biological samples

If a subject withdraws consent to the use of donated biological samples, the samples will be disposed of/destroyed, and the action documented. If samples are already analysed, AstraZeneca is not obliged to destroy the results of this research.

As collection of the biological samples is an integral part of the study, then the subject is withdrawn from further study participation.

The Principal Investigator:

- Ensures subjects' withdrawal of informed consent to the use of donated samples is notified immediately to AstraZeneca and Sponsor's delegate
- Ensures that biological samples from that subject, if stored at the study site, are immediately identified, disposed of /destroyed, and the action documented
- Ensures that the subject and AstraZeneca are informed about the sample disposal.

AstraZeneca ensures the organisations holding the samples is/are informed about the withdrawn consent immediately and that samples are disposed of/destroyed and the action documented and returned to the study site.

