3.9.9 Procedures for discontinuation of a subject from investigational product

Discontinuation of IP does not necessarily mean discontinuation of follow-up or termination of study participation. Subjects who are discontinued from the IP should be followed up to continue to undergo all study-related visits/procedures for the full treatment period (Table 2) in order to support the final efficacy and safety analysis for anifrolumab (see Section 8). Subjects who discontinue IP earlier than 12 weeks before Week 52 will be followed until Week 52. Those discontinued within 12 weeks prior to Week 52 will need to have follow-up beyond Week 52 to complete a 12 week safety observation period after the last dose of IP administration.

Subjects who discontinue IP in the second year extension period will be followed until Week 104. Those discontinued within 12 weeks prior to Week 104 will need to have follow-up beyond Week 104 to complete a 12-week safety observation period after the last dose of IP administration.

The reason for premature discontinuation of IP will be documented in the source documents and recorded in the eCRF.

It is essential to collect as much data as possible for all subjects throughout the study and especially all potential endpoint events. Complete withdrawal from the study (ie, withdrawal of consent) has a direct negative impact on the potential validity of all study data and should be avoided wherever possible. If the subject permanently discontinues IP prior to their completion of the study and wishes to continue with only selected study assessments; prioritised assessments are listed in Section 4.2.2.

For subjects who wish to withdraw from the study completely refer to Section 3.9.4.

If a subject is withdrawn from study, see Section 3.10.

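### Protocol Section 5.7.9 ends study participation when sample consent is withdrawn, with no exception for samples the protocol itself makes optional

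*Protocol*

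**What the plan says.** Section 5.7.9 of the protocol opens with its trigger: "If a subject withdraws consent to the use of donated biological samples, the samples will be disposed of/destroyed, and the action documented". It then states the consequence: "As collection of the biological samples is an integral part of the study, then the subject is withdrawn from further study participation". Neither sentence separates mandatory from optional samples.

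The scope comes from the opening of Section 5.7: "Biological samples (blood, urine, and tissue) will be collected and may be analysed for exploratory biomarkers". The same paragraph adds: "The results from these investigations will not be reported in the CSR but in separate reports".

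Two kinds of sample are optional:

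- Tissue biomarkers, Section 5.7.5, headed as optional: "These tests are in addition to the standard evaluation of renal biopsies and require a separate ICF".
- Pharmacogenomic blood, Section 5.6.1: "The collection of blood for pharmacogenomic analyses is optional. A separate ICF is required for these samples". Section 5.6 adds that no genetic sample is mandatory.

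On retention, Section 3.9.9 says that complete withdrawal from the study "has a direct negative impact on the potential validity of all study data and should be avoided wherever possible". Section 5.1.1 says that a subject who refuses adjudication of the optional second biopsy continues in the study unaffected.

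**The concern.** The stated reason for removal is that the samples are integral. That cannot be true of a sample a subject may decline at entry and still be randomised. As worded, someone who agrees to tissue work and later changes their mind is worse off than someone who never agreed.

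The trigger is consent to use. Section 5.7.8 allows retained samples to be kept for up to 15 years for later analysis, so an objection to storage alone could set the rule off.

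At stake are avoidable missing outcomes in a trial of about 150 subjects, where withdrawn subjects are not replaced (Section 3.9.6), and the loss of scheduled safety visits in subjects who did not ask to leave.

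**Working it through.** **1. The provisions side by side**

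| Place | Sample or event | Consequence for participation |
|---|---|---|
| Protocol 5.7.9 | Consent to use of donated samples withdrawn, no distinction made | Subject leaves the study |
| Protocol 5.7.5 | Tissue biomarkers, optional, separate consent | None stated; lies inside Section 5.7 |
| Protocol 5.6.1 | Pharmacogenomics, optional, separate consent | None stated; outside 5.7, caught only if donated samples is read broadly |
| Protocol 5.1.1 | Adjudication of second biopsy refused | Subject continues |
| Protocol 9.2 | Monitor's duties when sample consent is withdrawn | Reporting, disposal and documentation; study withdrawal not mentioned |
| Protocol 3.9.9 | Complete withdrawal in general | To be avoided wherever possible |

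The conflict is firm for tissue biomarkers, because 5.7.5 and 5.7.9 belong to the same section and tissue is named in its scope. For pharmacogenomics it rests on inference.

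**2. What a removal before Week 52 costs**

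- *Primary endpoint.* 24-hour UPCR is scheduled at Weeks 12, 24, 36 and 52 (Protocol 5.1). The Week 52 value is lost unless a closing visit falls in the Week 52 window. On-treatment values already collected stay in the MMRM (SAP 4.1.4.1 and 4.2.1).
- *CRR.* SAP 4.1.4.3 counts study withdrawal as premature discontinuation and imputes non-response. The exemption in SAP 4.1.3 for subjects dosed in the Week 48 window requires a Week 52 visit.
- *Safety.* The scheduled visits up to 12 weeks after the last dose are lost. Section 3.9.6 has AEs followed outside the study, and Section 4.2.2 asks for attempts at a discontinuation visit before consent is withdrawn. Both are written for withdrawal from the study, not for sample consent.

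A removal in the second year loses later data but not the Week 52 value.

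**3. Size**

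Inputs from Protocol 8.2: 50 per arm (pooled 100 versus placebo 50), ratio 0.65, log-scale SD 0.8, two-sided alpha 0.049.

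- SE = 0.8 × √(1/50 + 1/100) = 0.1386.
- |ln 0.65| / SE = 0.4308 / 0.1386 = 3.109.
- Critical value at alpha 0.049 = 1.969.
- Power = Φ(3.109 − 1.969) = Φ(1.140) = 87.3%. A noncentral-t calculation gives 86.9%. Both agree with the stated figure of about 86%.

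The documents give no rate of sample-consent withdrawal. Assume a share L of Week 52 values is lost equally in all arms and, conservatively, that those subjects contribute nothing. Then power = Φ(3.109 × √(1 − L) − 1.969):

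| Assumed loss | Subjects of 150 | Power |
|---|---|---|
| 0% | 0 | 87.3% |
| 1% | 1.5 | 87.0% |
| 2% | 3 | 86.6% |
| 5% | 7.5 | 85.6% |
| 10% | 15 | 83.7% |

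For CRR, one removed subject who would have responded lowers the placebo rate by 1/50 = 2 percentage points, or the pooled anifrolumab rate by 1/100 = 1 point. A subject who would not have responded changes nothing.

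**The case against.** The best defence is that the rule limits itself: it applies because collection is integral, and optional samples are not integral. On that view, revoking a separate optional consent leaves the main consent intact, as Section 5.1.1 does for the second biopsy. The consent forms, which might say so, are not among the documents reviewed. This is a sensible reading of intent, but not what the text says. Section 5.7.9 asserts that collection is integral and draws the consequence; it does not make the consequence conditional on the sample being integral. A site applying it literally would remove the subject.

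Other parts of the defence stand:

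- Serum, plasma, urine and RNA samples are not marked optional. The sponsor may make them a condition of participation, and the documents do not show that to be an error.
- Section 5.7 also holds the 4-gene IFN test (5.7.4), a stratification factor in the primary and CRR analyses. A reader might infer that everything under 5.7.9 is dispensable exploratory material; that is not so.
- Section 3.9.9 states an aim, not a prohibition.
- The rule's absence from Section 3.9.4 proves little: that list concerns stopping IP, and the subject-decision item includes an open category.
- The CRR tipping-point analysis (SAP 4.2.2) revisits subjects imputed as non-responders after stopping IP early without restricted medication, so the imputation would not go unexamined.

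**Conclusion.** The point holds as a defect of wording with a practical consequence: read literally, Section 5.7.9 removes a subject for withdrawing consent to a sample the protocol calls optional. This is certain for tissue biomarkers and arguable for pharmacogenomics. It runs against the aim in Section 3.9.9 and the approach in Section 5.1.1.

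The size is small. No rate is given, few subjects are likely to be affected, and the power cost is about 0.3 percentage points at an assumed 1% loss and 1.7 points at 5%.

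A reader might infer that the rule threatens the primary analysis or leaves these subjects with no safety follow-up. The documents support neither. Earlier UPCR values remain in the model, power stays close to the stated 86% at low loss rates, and Sections 3.9.6 and 4.2.2 provide some follow-up. The case for change is that the missing data and lost visits serve no purpose and are nearly free to avoid.

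**What to change.** Amend Section 5.7.9 in two respects:

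1. Withdrawing consent for optional samples (tissue biomarkers under 5.7.5, pharmacogenomics under 5.6.1) stops their collection and triggers destruction of those samples only. The subject stays in the study with all scheduled efficacy and safety assessments.
2. Study withdrawal under 5.7.9 applies only to samples that are a condition of participation, and the section lists them. The sponsor should say explicitly whether serum, plasma, urine and RNA samples are on that list.

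Bring the main and optional consent forms into line. The cost is a paragraph of protocol text, matching consent wording, and a few subjects without optional exploratory samples.
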